5.2.1. Analyses for Binary Endpoints

Binary data will be summarized using number of unique participant incidence, proportion in the analysis set, and the 2-sided 95% exact confidence interval for the proportions. The confidence interval will be based on the Clopper-Pearson exact method.

Binary data in this study include complete response (CR), partial response (PR), stable disease (SD), progressive disease (PD), and objective response rate (ORR), based on RECIST 1.1 and irRECIST.

5.2.2. Analyses for Continuous Endpoints

Continuous data will be summarized with the mean, median, minimum, maximum, standard deviation, and 2-sided 95% confidence interval of the mean if the sample size permits and deemed necessary.

Continuous data in this study include, but not limited to, certain laboratory measurements, vital signs, ECG, certain PK parameters or biomarkers.

5.2.3. Analyses for Categorical Endpoints

Categorical data will be summarized by number of unique participant incidence and proportion of participant in each category, and 2-sided 95% confidence interval of the proportion if the sample size permits and deemed necessary.

An example of categorical data presentation is adverse events or laboratory abnormalities graded by NCI CTCAE v5.0, where each grade is considered as a category.

5.2.4. Analyses for Time-to-Event Endpoints

The time-to-event endpoints will be summarized using the Kaplan-Meier method and estimated survival curves may be displayed graphically when needed. Graphs will describe the number of participants at risk over time. The median, quartiles, and probabilities of an event at particular points in time will be estimated by the Kaplan-Meier method, when possible based on the number of observed events. Confidence intervals for medians and quartiles, based on the Brookmeyer-Crowley method (Brookmeyer and Crowley, 1982), may be presented. Confidence intervals for the estimated probability of an event at a particular time point may be generated using the Greenwood formula.

Time to event endpoints include duration of response(DoR), progression-free survival (PFS), and overall survival (OS) when the event numbers are sufficient for reasonable interpretation.

5.3. Methods to Manage Missing Data

For the analysis of safety endpoints, the sponsor data standard rules for imputation will be applied based on the Safety Rulebook.

5.3.1. Missing Dates

In compliance with Pfizer standards, if the day of the month is missing for any date used in a calculation, the 1st of the month will be used to replace the missing date unless the calculation results in a negative time duration (eg, date of onset cannot be prior to day one date). In this case, the date resulting in 0 time duration will be used. Pfizer standards are also used if both month and day are missing (Jan 1 unless negative time duration). This excludes the pharmacokinetic and ECG analyses, which will only use the actual date collected or if date not available deem the data missing.

5.3.2. Efficacy Analysis

For tumor assessment that will be used in the binary efficacy endpoint, every effort will be made to retrieve data in the CRF, however missing data will be left as is, no imputation will be performed. The reasons for missing tumor assessment will be collected

For the time-to-event endpoints, the missing data handling method will be censoring. Censoring rules for time-to-event endpoints are detailed in [Section 6.2.2](#).

5.3.3. Pharmacokinetics

5.3.3.1. Concentrations Below the Limit of Quantification

In all data presentations (except listings), concentrations below the limit of quantification (BLQ) will be set to zero. (In listings BLQ values will be reported as “<LLQ”, where LLQ (i.e. lower limit of quantification) will be replaced with the value for the LLQ.)

5.3.3.2. Deviations, Missing Concentrations and Anomalous Values

Participants who experience events that may affect their PK (eg, incomplete dosing) may be excluded from the PK analysis.

In summary tables and plots of median profiles, statistics will be calculated having set concentrations to missing if 1 of the following cases is true:

1. A concentration has been collected as ND (i.e., not done) or NS (i.e., no sample),
2. A deviation in sampling time is of sufficient concern or a concentration has been flagged anomalous by the pharmacokineticist.

Note that summary statistics will not be presented at a particular time point if more than 50% of the data are missing.

An anomalous concentration value is one that, after verification of bioanalytical validity, is grossly inconsistent with other concentration data from the same individual or from other subjects. For example, a BLQ concentration that is between quantifiable values from the same dose is considered as anomalous. Anomalous concentration values may be excluded from PK analysis at the discretion of the PK analyst.

5.3.4. Pharmacokinetic Parameters

Actual PK sampling times will be used in the derivation of PK parameters. If a PK parameter cannot be derived from a subject's concentration data, the parameter will be coded as NC (i.e., not calculated). (Note that NC values will not be generated beyond the day that a subject discontinues.)

In summary tables, statistics will not be presented for a particular treatment group if more than 50% of the data are NC. For statistical analyses, PK parameters coded as NC will also be set to missing.

If an individual subject has a known biased estimate of a PK parameter (due for example to dosing error), this will be footnoted in summary tables and will not be included in the calculation of summary statistics or statistical analyses.

5.3.5. Pharmacodynamic Parameters

Missing data for the pharmacodynamic parameters will be treated as such and no imputed values will be derived.

5.3.6. QTc

For the corrected QT (QTc) analyses, no values will be imputed for missing data.

5.4. Statistical Considerations of COVID-19 Impacted Data

In March 2020, the World Health Organization (WHO) announced a global pandemic of the virus SARS-CoV-2 and the resulting disease COVID-19. During the conduct of this trial, if any participant's data is impacted by this pandemic, the following considerations will be given in the data analyses:

- a. If a participant dropped out of the study during the DLT evaluation window in Parts 1A and 1B due to COVID-19, a replacement participant may be added.
- b. Death caused by COVID-19 is still considered as an "event" in the analysis of PFS (Parts 1 and 2) and OS (Part 2). If deemed necessary, a sensitivity analysis may be performed where COVID-19 driven death is censored at the death date.
- c. If a scheduled tumor radiographic scan is *delayed* out of the Schedule of Activity allowable window, or is *missing* (i.e. participant skipped a scheduled tumor radiographic scan) due to any reasons related to the pandemic, this delay or missingness does not alter the censoring rules for PFS or TTP as described in [Section 6.2.2](#). A censoring reason of "COVID-19" may be added to the PFS or TTP summary if the specific reason of tumor scan delay or missing can be attributed to COVID-19. If deemed necessary, a sensitivity analysis may be performed where participants would be censored on the date of COVID-19 diagnosis.

In the confirmed ORR analysis, as described in [Section 6.2.2](#), if a response can't be confirmed by a subsequent tumor scan because of the pandemic (i.e. the subsequent tumor scan wasn't performed), then the initial response will be considered as

- unconfirmed. This is a conservative approach. No sensitivity analysis will be performed.
- d. Any COVID-19 related symptoms are to be captured as adverse events in the case report form. Those adverse events will be summarized in the same manner as other adverse events. If a label or phrase of COVID-19 can be identified in the investigator provided adverse event term, then a separate AE listing may be provided for just the COVID-19 related events.
 - e. If identifiable, the COVID-19 related data points, including missing data where the reason of missing is identified as COVID-19 related (site closure hence data could not be captured; participants skipped a visit because of concern over the pandemic), protocol deviations driven by COVID-19, safety events caused by COVID-19 may be separately listed.

6. ANALYSES AND SUMMARIES

6.1. Primary Endpoints for Part 1

6.1.1. Dose-Limiting Toxicities (DLTs)

- Analysis set: Per protocol analysis set.
- Analysis methodology:

For the purpose of dose escalation, the DLT observation period will be during the first cycle (28 days after the start of study treatment), or DLT window, in each participant. According to the design, cohort sizes are planned to be approximately 3, but it is required to have at least 2 DLT-evaluable patients in the dosing cohorts. The participants who cross over from Part 1A monotherapy to Part 1B combination therapy will be excluded from the DLT assessment in Part 1B.

Whether an adverse event a participant experienced during the DLT window is determined as a DLT or not is based on the DLT definitions provided in Section 4.3.3 of the protocol. A DLT yes/no checkbox will be provided in the case report form, where the investigator provides his/her judgement if an event is a DLT or not. However, the final determination will be reached between the investigators and the sponsor during the dose level review meeting (DLRM). These final decisions will be documented.

The DLT events will be summarized by dose level. A listing of the DLTs events will also be provided in which the participant primary diagnosis (malignancy), dose level the participant was enrolled to, DLT event start day and stop day relative to the cycle 1 day 1 dose date, the DLT event term, NCI CTCAE grade, relatedness to the investigational product (PF-07265028), or sasanlimab (Part 1B), outcome of the event, along with other variables deemed important, will be included.

- Missing data: All enrolled participants in Part 1 should have an indicator variable derived to be either 1 (yes) or 0 (no) based on the DLT definitions and participant's

safety data during the DLT observation window. If a participant fails to have a value on the indicator variable because the participant being non-DLT-evaluable, the participant may be replaced.

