4.3.3. DLT Definition

A participant is classified as DLT-evaluable if the participant either 1) received at least 75% of the planned doses of the study intervention and have received all scheduled safety assessments during the DLT-observation period (Cycle 1 [28 days]) or 2) have experienced a DLT regardless of the percentage of planned doses received. The percentage of drug received is calculated as the percentage of the actual total amount of drug(s) administered during the DLT-observation period in relation to the planned total amount of drug(s) to be administered for the DLT-observation period. If a participant fails to meet these criteria, the participant is deemed non-evaluable for a DLT, and may be replaced. The sole exception to criterion 1 above is if the participant has missed a minority of safety assessments due to emergency situations (eg, site accessibility issues, inability to go to an external lab, etc). In such cases, the DLRM Committee may judge the participant evaluable, depending on the abundance of the available data.

For the purpose of dose escalation, all treatment-emergent AEs meeting the definition of DLT occurring in the first cycle of treatment (within 28 days of the first dose or until the participant receives the first dose of the second treatment cycle in the event of treatment delays) will be considered DLTs unless they are clearly attributable to underlying disease or intercurrent illness.

Severity of AEs will be graded according to CTCAE version 5.0. For those AEs involving a worsening of a baseline abnormality, a DLT must represent a clinically significant (in the opinion of the Investigator after discussion with the sponsor) shift from baseline.

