6.1.1. Administration

6.1.1.1. PF-07265028

Participants will swallow PF-07265028 tablets whole with at least 8 ounces (240 mL) of water, and will not manipulate or chew the study intervention prior to swallowing. PF-07265028 will initially be administered QD by mouth for all cohorts on a continuous basis. Participants who are unable to swallow whole tablets may dissolve their dose in oral syringe(s) as outlined in the IP manual to allow for suspension administration either orally or via an NG tube. If supported by emerging data, BID continuous regimen may be considered. A cycle is defined as 28 days, regardless of missed doses or dose delays.

Participants will take PF-07265028 at approximately the same time within each dosing interval (ie, ± 3 hours of nominal time). On site visit days, participants will take the drug at the site after performing predose assessment. On other days, participants will be instructed to self-administer the drug at home. A dosing diary will be given to each participant to support at home dosing. The participants will be requested to note the date and time of each dose, food consumption status at the time of drug administration.

If a participant misses a dose at the scheduled time, the participant can still take the dose within 4 hours of the scheduled time. If the participant missed taking a dose after 4 hours of the scheduled time, or day of treatment, they must be instructed not to “make it up” but resume subsequent doses as prescribed. This dose will be considered as a missed dose. In addition, if a participant vomits any time after taking a dose, they should not “make it up” but to resume subsequent doses as prescribed. Lastly, if a participant inadvertently takes 1 extra dose during a day, the participant should not take the next dose of PF-07265028.

Food Requirements (Except for the Food-Effect Subset or Cohorts Evaluating Food Intake on Tolerability)

Participants will take PF-07265028 orally with at least 8 oz (240 mL) of water on an empty stomach. No food or liquids other than water will be consumed for 2 hours before and 2 hour following each dose throughout the study).

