6.1.1.2. Sasanlimab (PF-06801591)

For participants in Part 1B and Part 2, qualified and trained investigator site personnel will administer sasanlimab at a fixed dose. See [Section 8.2.7](#) for local site injection tolerability assessment. In the investigational combination therapy with PF-07265028, sasanlimab 300 mg (50 mg/mL), will be administered SC Q4W to the abdomen. Sasanlimab should be administered to 2 or more different quadrants of the abdomen (with preference given to the lower quadrants when possible); 1 or 2 injections per quadrant. If SC injections in the abdominal location are not possible, SC injections can be administered in a distributed manner in the thighs. SC injections in the upper extremities (eg, deltoid, upper and lower arm) are not permitted. Sasanlimab SC injection will be administered at least 30 minutes after administration of PF-07265028. Additional guidance on SC injection site locations is provided in [Appendix 16 Section 10.16](#). For specific instructions on the handling and preparation instructions of study intervention, refer to the Product Specific IP manual. See [Section 8.2.7](#) for local site injection tolerability assessment.

Study staff should refer to the IP manual for specific instructions on the preparation and handling of the study intervention.

A cycle is defined as the time from Day 1 dose to the next Day 1 dose. Participants will receive a single dose of sasanlimab on Day 1 of each cycle.

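### The SAP closes the DLT window at 28 days, but the protocol keeps it open until a delayed first Cycle 2 dose, so the same late event can be a DLT in one document and not in the other

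*SAP*

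**What the plan says.** Protocol 4.3.3 sets the counting rule for dose escalation. The basic span for qualifying treatment-emergent events is 28 days from first dose. When treatment is delayed, counting goes on "until the participant receives the first dose of the second treatment cycle in the event of treatment delays". Such events "will be considered DLTs unless they are clearly attributable to underlying disease or intercurrent illness".

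SAP 6.1.1 sets a window for the same purpose: "the DLT observation period will be during the first cycle (28 days after the start of study treatment"). It has no clause for delays. It takes the DLT criteria from Protocol 4.3.3, but the question it puts to them is limited to its own window: "Whether an adverse event a participant experienced during the DLT window is determined as a DLT or not". Each participant's 0/1 DLT indicator is likewise derived from safety data inside that window.

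The primary estimand (Protocol 9.1.1.1, SAP 2.1.1) ties the evaluation period to Cycle 1 without giving its length. The protocol describes that length in several ways:

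- 4.3.3, for evaluability: "DLT-observation period (Cycle 1 [28 days"]).
- 6.1.1.1, for PF-07265028: "A cycle is defined as 28 days, regardless of missed doses or dose delays".
- 6.1.1.2, for sasanlimab: "A cycle is defined as the time from Day 1 dose to the next Day 1 dose".
- 6.5.4: if an interruption runs past Day 28, the restart day becomes Day 1 of the next cycle.

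**The concern.** First-cycle DLTs are the Part 1 primary endpoint and the main data that the BLRM uses to decide which dose may be given next. The two windows differ only for participants whose Cycle 2 is delayed, and toxicity is a common reason for delay. The SAP window lies wholly inside the protocol window, so the disagreement runs one way: the SAP reading can drop a DLT but never add one.

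A dropped event need not take the participant out of the analysis. Someone who received at least 75% of planned doses and completed the safety assessments stays evaluable and enters the model as a participant without a DLT. The DLT rate is then pushed down and the recommended dose up.

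**Working it through.** **1. The passages applied to one case (hypothetical).** A participant on daily dosing is held from Day 27 for toxicity. Grade 4 thrombocytopenia, a DLT under Protocol 4.3.3.1, starts on Day 32, before any Cycle 2 dose.

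- Doses received: 26 of 28, and 26/28 = 92.9%, above the 75% needed for evaluability.
- Protocol 4.3.3: treatment is delayed and Day 32 precedes the first Cycle 2 dose, so this is a DLT.
- SAP 6.1.1, read literally: Day 32 is after Day 28, so the indicator is 0.

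**2. Possible length of the gap.** Protocol 6.5.3 allows holds of up to 4 weeks for PF-07265028 and up to 8 weeks for sasanlimab. A 4-week delay takes the protocol window to about Day 28 + 28 = Day 56. If a sasanlimab hold delays Cycle 2, it could reach about Day 28 + 56 = Day 84. The SAP window ends at Day 28 in both cases.

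**3. Effect on the dose decision.** Inputs from Protocol Appendix 11 and 9.3.2:

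- Model: logit π(d) = log α + β·log(d/600).
- Prior: log α has mean logit(0.2) = −1.386 and SD 2; log β has mean 0 and SD 1; correlation 0.
- Likelihood: the product over doses of π^r·(1−π)^(n−r), for r DLTs in n participants.
- Overdose control: a dose is allowed if P(π ≥ 0.33 | data) < 0.25.
- Cohort size: about 3 (SAP 6.1.1). The DLT counts below are assumed.

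Numerical integration on a 1601 × 1601 grid first reproduces the prior overdose probabilities in Table 16 (computed / stated):

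- 25 mg: 0.071 / 0.071
- 50 mg: 0.092 / 0.091
- 80 mg: 0.112 / 0.109
- 125 mg: 0.137 / 0.135
- 200 mg: 0.174 / 0.171
- 320 mg: 0.230 / 0.230
- 500 mg: 0.316 / 0.317

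All agree within 0.003, and the 25 mg value is the 7.1% quoted in Protocol 9.3.2.

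One late event is then moved from non-DLT (SAP window) to DLT (protocol window).

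The decision reverses:

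- 25 mg, 0/3 versus 1/3: overdose risk at 50 mg 0.019 versus 0.329.
- 0/3 at 25 mg, then 50 mg, 1/3 versus 2/3: risk at 80 mg 0.159 versus 0.492.
- 0/3 at 25 and 50 mg, then 80 mg, 1/3 versus 2/3: risk at 125 mg 0.111 versus 0.370.

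The decision does not reverse:

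- 0/3 at 25 mg, then 50 mg, 0/3 versus 1/3: risk at 80 mg 0.009 versus 0.159.
- 0/3 at 25 and 50 mg, then 80 mg, 0/3 versus 1/3: risk at 125 mg 0.007 versus 0.111.
- 0/3 at 25, 50 and 80 mg, then 125 mg, 0/3 versus 1/3: risk at 200 mg 0.010 versus 0.120.
- 0/3 at 25 and 50 mg, then six participants at 80 mg, 1/6 versus 2/6: risk at 125 mg 0.049 versus 0.201.

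Protocol 4.3.2 lets a slightly higher threshold, for example 30%, be considered. The three reversing values (0.329, 0.492, 0.370) exceed that as well.

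**The case against.** The best defence is that the SAP inherits the protocol's rule. SAP 2.1.1 and 6.1.1 both point to Protocol 4.3.3 for the DLT definition. Both documents also say that a major change to a primary endpoint definition will appear in a protocol amendment, so the SAP is not meant to override 4.3.3 silently. Under Protocol 6.5.4 the first cycle can be read as including the hold, with 28 days as its nominal length. This makes an intended override unlikely, but it does not settle the window: SAP 6.1.1 states its own window and applies 4.3.3 only to events inside it.

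A second defence is that people, not the model alone, decide. The dose level review meeting makes the final DLT determination. Investigators and sponsor may choose a dose below the model's recommendation. Appendix 11 also lets some AEs that are not protocol DLTs enter the BLRM at weight 0.5, and this could become the primary escalation method. So DLTs are the main model input, not the only one. This stands as mitigation, but no text tells the meeting which window to use.

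A third is that the affected group is narrow: no DLT by Day 28, Cycle 2 delayed, then a new qualifying event before redosing. Some holds are already DLTs because toxicity prevented delivery of 75% of doses. This also stands, and it limits how often the conflict matters.

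A reader might also infer that events with a duration criterion, such as Grade 3 fatigue lasting at least 5 days, are lost under the SAP when they start in the last week. The documents do not support this as a conflict. The SAP covers events experienced in the window and does not require the duration to be completed by Day 28. The protocol leaves the same question open for a participant with no delay.

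**Conclusion.** The inconsistency is real and should be fixed. For a qualifying event starting after Day 28 and before a delayed first Cycle 2 dose, Protocol 4.3.3 and the literal text of SAP 6.1.1 give opposite classifications, and the SAP's can only lower the DLT count. It is not purely SAP against protocol, because the protocol's own evaluability wording and its cycle definitions disagree too.

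A reader might infer that losing any single DLT changes the escalation decision. The calculations do not support that. A late event at the starting dose, or a second DLT in a cohort of three at 50 or 80 mg, reverses the decision. A first DLT at 50, 80 or 125 mg after clean lower cohorts does not.

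These figures rest on assumed DLT counts, cohorts of 3 (one example uses 6) and the Part 1A prior. The Part 1B model is in a Technical Supplement that is not among these documents, so nothing is claimed for it. The frequency of Cycle 2 delays is not stated, so the expected bias cannot be given a size.

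**What to change.** Reconcile SAP 6.1.1 and 2.1.1 with Protocol 4.3.3, 9.1.1.1, 6.1.1.1, 6.1.1.2 and 6.5.4, so that one DLT window is used for counting DLTs, for evaluability and for the BLRM input. Which window to adopt is for the sponsor and investigators to decide. Editing the SAP alone would leave the 28-day evaluability wording and the differing cycle definitions in place.

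Two additions are needed whichever window is chosen:

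- Assign events to the window by onset date, so that an event starting inside it that later meets a duration criterion is counted.
- If the delay extension is kept, state when the window ends for a participant who never receives a Cycle 2 dose, since the present protocol wording gives no end for that case.

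The cost is wording in both documents, with a protocol amendment for the protocol text. If the extension is kept, the dose-level review may have to wait for the length of a hold, up to 4 weeks for PF-07265028 or 8 weeks for sasanlimab. If it is dropped, the protocol should say openly that events during a Cycle 2 delay are not DLTs and how they are considered in the dose decision.
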